# 8.6 Other Reasons for Treatment Postponement

Study drug administration may be delayed for medical or other reasons (e.g., social reasons, weather circumstances). In case of a delay in study drug administration, the treatment should be restarted as early as possible. Should treatment be delayed for more than 14 days after the missed dose, then the treatment should be permanently discontinued. The subject should continue with the first follow-up visit in the study.

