## 10.1.12 Follow-Up Visits

## Follow-Up Visit 1:

After treatment discontinuation without disease progression a follow-up visit will occur 4 weeks  $(\pm 2 \text{ days})$  after the last dose of study drug.

At this visit, the following will be obtained, performed, or assessed:

- Toxicity/AE assessment since the last visit
- Concomitant medications
- Karnofsky performance status
- Blood sample for hematology, serum chemistry, coagulation, βHCG pregnancy test for women of childbearing potential, endocrinology, anti-MOR03087 antibodies, serum M-protein, serum FLCs, pharmacokinetics (MOR03087), and B, T, and NK cells
- Sample from 24-hour urine for urine M-protein
- Response assessment. Note: all responses require two consecutive assessments, and should ideally be confirmed.
- Physical examination (including basic neurological examination of general motor and sensory systems, mental status, cranial nerves, and coordination)
- Body weight
- Quality of life questionnaires (QLQ-MY20 and QLQ-C30)
- 12-Lead ECG, if clinically indicated at the discretion of the investigator
- Vital signs (blood pressure, pulse rate, respiratory rate, and body temperature)

For subjects receiving POM or LEN, the additional following will be obtained, performed, or assessed:

• Clinical review of signs/symptoms for possible VTEs in subjects treated with POM or LEN. Subjects who develop symptomatic deep vein thrombosis will be assessed and diagnosed objectively by Doppler ultrasonography or a comparable method per institution's standard of care. See Appendix 18.9 for deep vein thrombosis and pulmonary embolism diagnostic algorithms

For women of childbearing potential with irregular cycles in study cohorts that include LEN or POM, a pregnancy test (serum or urine) is to be performed 14 days after treatment discontinuation.

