#### Follow-Up Visit 2 and Subsequent Follow-Up Visits:

Four weeks ( $\pm 2$  days) after Follow-up Visit 1, a second follow-up visit will occur. If there is still a response to therapy at this visit, then a follow-up visit will be repeated every fourth week ( $\pm 2$  days) until there is a disease progression (but no longer than 3 years), death, or the subject starts a new anti-myeloma therapy. Follow-up visits may be delayed for a maximum of 2 weeks after the normal visit window due to other reasons (e.g., logistical).

At each of these visits, the following will be obtained, performed, or assessed:

- Toxicity/AE assessment since the last visit
- Concomitant medication
- Karnofsky performance status
- Blood sample for hematology, serum chemistry, βHCG pregnancy test for women of childbearing potential, anti-MOR03087 antibodies (at Follow-up Visit 2 only), B, T, and NK cells, serum M-protein, and serum FLCs
- Sample from 24-hour urine for urine M-protein
- Response assessment, to be continued until disease progression or death or subsequent anti MM therapy start whatever occurs first. Note: all responses require two consecutive assessments, and should ideally be confirmed at the next follow-up visit.
- Physical examination (including basic neurological examination of general motor and sensory systems, mental status, cranial nerves, and coordination)
- Body weight
- Quality of life questionnaires (QLQ-MY20 and QLQ-C30)
- 12-Lead ECG, if clinically indicated at the discretion of the investigator
- Vital signs (blood pressure, pulse rate, respiratory rate, and body temperature)
- Clinical review of signs/symptoms for possible VTEs in subjects treated with POM or LEN. Subjects who develop symptomatic deep vein thrombosis will be assessed and diagnosed objectively by Doppler ultrasonography or a comparable method per institution's standard of care. See Appendix 18.9 for deep vein thrombosis and pulmonary embolism diagnostic algorithms

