- Serum M-protein and serum free light chains only at Day 1 (CxD1) of each cycle, starting with Cycle 3+
- Sample from 24-hour urine for urine M-protein only at Day 1 (CxD1) of each cycle, starting with Cycle 3+
- B, T and NK cells at Day 15 (CxD15) of each cycle, starting with Cycle 3+
- Blood sample for predose pharmacokinetics (MOR03087) and anti-MOR03087 antibodies every CxD15
- Response assessment on Day 1 of every cycle (CxD1), to be continued until disease progression or death or subsequent anti MM therapy start whatever occurs first. Note: all responses require two consecutive assessments, and should ideally be confirmed at Day 1 of the next cycle

- Physical examination (including basic neurological examination of general motor and sensory systems, mental status, cranial nerves, and coordination)
- Body weight
- Vital signs (blood pressure, pulse rate, respiratory rate, and body temperature immediately before infusion)
- Premedication (at the investigator's discretion if no infusion reaction during Cycle 1)

For subjects receiving POM or LEN, the additional following will be obtained, performed, or assessed prior to study drug administration:

- 12-lead ECG
  - For subjects treated in Part D (POM), 12-lead ECG monitoring will be performed on Cycle 3 Day 1, and on Day 1 of every third cycle thereafter (Cycles 3, 6, 9, etc.), and at treatment discontinuation. Subjects with QT prolongation (or borderline QT prolongation) but otherwise non-clinically significant will require more frequent ECG monitoring at the discretion of the investigator.
  - For subjects treated in Part E (LEN), 12-lead ECG will be performed at each visit during treatment if clinically indicated per investigator's judgment, and at treatment discontinuation if clinically indicated per investigator's judgment
- Clinical review of signs/symptoms for possible VTEs in subjects treated with POM or LEN. Subjects who develop symptomatic deep vein thrombosis will be assessed and diagnosed objectively by Doppler ultrasonography or a comparable method per institution's standard of care. See Appendix 18.9 for deep vein thrombosis and pulmonary embolism diagnostic algorithms
- Prophylactic treatment of thromboembolism for subjects enrolled into the LEN or POM cohorts

Study drug administration:

- MOR03087 study drug administration

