3. STUDY METHODS

3.1 Overall Study Design and Plan

This is an open-label, multicentre, standard 3+3 dose-escalation study designed to characterize the safety profile and to assess the preliminary efficacy of MOR03087 in adult subjects with relapsed or refractory MM as monotherapy and in combination with DEX or standard IMiD therapy (POM and LEN). Approximately 10-15 sites will participate in this study.

The MTD and/or recommended dose and dosing regimens will be confirmed in a confirmation cohort of at least 6 subjects. A total of up to 126 subjects may participate in the study (including dose escalation and confirmation cohorts).

In each cohort, 28-day cycles will be used.

An independent Data Monitoring Committee (DMC) will review the relevant safety information before considering dose escalation for the next cohort.

Part A: MOR03087 dose escalation (bi-weekly treatment - q2w):

Up to 8 dose levels of MOR03087 will be evaluated:

- Cohort 1 - Dose level 1: 0.01 mg/kg
- Cohort 2 - Dose level 2: 0.04 mg/kg
- Cohort 3 - Dose level 3: 0.15 mg/kg
- Cohort 4 - Dose level 4: 0.5 mg/kg
- Cohort 5 - Dose level 5: 1.5 mg/kg
- Cohort 6 - Dose level 6: 4.0 mg/kg
- Cohort 7 - Dose level 7: 8.0 mg/kg
- Cohort 8 - Dose level 8: 16.0 mg/kg

Each 28-day cycle will consist of:

MOR03087 infusion on Day 1 and Day 15 of the cycle. In Cycle 1, a loading dose will additionally be administered on Day 4 of the cycle.

At least 48 hours will pass between the first study drug administration to the subjects within a cohort in order to observe for AEs.

Part B: MOR03087 dose escalation (weekly treatment - q1w):

- Dose level 6b: 4.0 mg/kg
- Dose level 7b: 8.0 mg/kg
- Dose level 8b: 16.0 mg/kg

Each 28-day cycle will consist of:

MOR03087 infusion on Days 1, 8, 15, and 22 of the cycle. In Cycle 1, a loading dose will additionally be administered on Day 4 of the cycle.

Part C: MOR03087 dose escalation (weekly/biweekly treatment - q1w/q2w) plus low dose of DEX:

- Dose level 6c: 4.0 mg/kg
- Dose level 7c: 8.0 mg/kg
- Dose level 8c: 16.0 mg/kg

Each 28-day cycle will consist of:

MOR03087 infusion on Days 1, 8, 15, and 22 of the cycle. In Cycle 1, a loading dose will additionally be administered on Day 4 of the cycle.

Only for dose level 8c, for cycle 4 and onwards each 28-cycle will consist of: MOR03087 infusion on Day 1 and 15 of the cycle.

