Death from other causes than disease progression, without documented disease progression before	Date of last tumor assessment	Censored
Death caused by disease progression between adequate assessments	Date of death	Progressed
Death caused by disease progression or progression after > 65 days (2x 29-day cycle +7 days) after last tumor response assessment (representing the time interval of 2 or more consecutive missed tumor response assessments)	Date of last tumor assessment	Censored

Progression-free survival (PFS): Progression-free survival will be defined as the time from

Cycle 1, Day 1 until date of progression (as defined above) or date of death, whatever occurs earlier, or date of censoring (as defined below). For censoring rules see Table 3.

Table 3: Censoring Rules for PFS

Situation	Date of Progression or Censoring	Outcome
Disease progression	Date of progression	Progressed
No post-baseline tumor assessment	Date of first treatment	Censored
No disease progression	Date of last tumor assessment	Censored
Subject received non-study MM treatment before disease progression	Date of last tumor assessment prior to non-study treatment	Censored
Death before any date of PD assessment	Date of death	Progressed
Death between adequate assessments	Date of death	Progressed
Death or progression after > 65 days (2x 29-day cycle +7 days) after last tumor response assessment (representing the time interval of 2 or more consecutive missed tumor assessments)	Date of last tumor assessment	Censored

Additional time to event variables:

Duration of clinical benefit (DoCB): The duration of clinical benefit will be calculated in the subgroup of subjects showing confirmed sCR, CR, VGPR, PR or MR. Duration of clinical benefit will be defined as the time from date of first clinical benefit (sCR, CR, VGPR, PR or MR) until date of progression or death due to progression (as defined above), whichever is documented first. For censoring rules see Table 2.

Additionally, the DoR of sCR/CR and sCR/CR/VGPR according to the above defined rules will be reported separately.

Time to next treatment (TTNT): TTNT will be defined as the time from Cycle 1, Day 1 until start date of new anti-MM treatment as documented at the end of trial visit under “Subsequent anti-MM Treatment” or date of death. Subjects with no documented start date for a subsequent anti-MM treatment and no documented date of death will be considered censored using the date of the last visit.

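### The 65-day censoring limit, which the SAP equates with two or more missed assessments, is passed after one missed visit when a subject moves from treatment to follow-up

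*SAP*

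**What the plan says.** SAP 7.3.3.3 gives the censoring rules. The last row of Table 3 (PFS) covers "Death or progression after > 65 days (2x 29-day cycle +7 days) after last tumor response assessment" and glosses it as "representing the time interval of 2 or more consecutive missed tumor assessments". Such a subject is censored at the last tumor assessment. The last row of Table 2 (DoCB, DoR, TTP) does the same for "Death caused by disease progression or progression after > 65 days (2x 29-day cycle +7 days) after last tumor response assessment".

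The assessment schedule is in the protocol:

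- During treatment, response is assessed on Day 1 of each cycle (Tables 1 and 2 of section 7.1; section 10.1.13).
- On stopping, the reference point changes to the last dose: "After treatment discontinuation without disease progression a follow-up visit will occur 4 weeks" (± 2 days) after it (section 10.1.12).
- Visit 2 follows 4 weeks (± 2 days) after visit 1, and later visits come every fourth week. The text on visit 2 and later visits allows a delay of up to 2 weeks beyond the window.
- On treatment, section 8.6 tolerates postponement up to a limit: "Should treatment be delayed for more than 14 days after the missed dose, then the treatment should be permanently discontinued".

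On cycle length, SAP 3.1 states "In each cohort, 28-day cycles will be used", whereas the 65-day figure is built on 29 days.

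**The concern.** A fixed number of days can stand in for a count of missed visits only if visits are evenly spaced. They are not when treatment ends: the last on-treatment assessment is tied to Day 1 of the final cycle, and the next is tied to the last dose, which may come two or three weeks after that Day 1. The interval is longer than a cycle before any visit has been missed, so one missed visit may be enough to exceed the limit.

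A subject in that position who progresses or dies loses the event and is censored at the last on-treatment assessment. Dropping such events tends to raise the Kaplan-Meier estimates beyond the date of the lost event. PFS, TTP, DoR and DoCB are all exposed. For the last three, the only deaths concerned are those due to progression.

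**Working it through.** **The SAP's figure.** 2 × 29 + 7 = 65 reproduces. With the 28-day cycle the same formula gives 2 × 28 + 7 = 63.

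**Regular 28-day spacing.** The gap is 28 × (missed + 1), with ± 2 days on each of the two visits.

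- One missed: 28 × 2 = 56, at most 56 + 4 = 60.
- Two missed: 28 × 3 = 84, at least 84 − 4 = 80.

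A limit of 65 lies between 60 and 80 and separates the two cases correctly.

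**Treatment to follow-up.** Inputs: infusions on Days 1, 8, 15 and 22 of a weekly cycle, or on Days 1 and 15 of a bi-weekly cycle (Protocol 7.1); visit 1 at last dose + 28 days; visit 2 at visit 1 + 28 days. The gap from Day 1 of the final cycle to visit 1 is (last dose day − 1) + 28. If visit 1 is missed, the gap to visit 2 is 28 days more. The ranges use ± 2 days for each follow-up visit.

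| Last dose | To visit 1, none missed | To visit 2, visit 1 missed | Over 65? |
|---|---|---|---|
| Day 22 | 21 + 28 = 49 | 49 + 28 = 77 (73–81) | Yes, whole range |
| Day 15 | 14 + 28 = 42 | 42 + 28 = 70 (66–74) | Yes, whole range |
| Day 8 | 7 + 28 = 35 | 35 + 28 = 63 (59–67) | Not nominally |
| Day 1 | 0 + 28 = 28 | 28 + 28 = 56 (52–60) | No |

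Calendar example: Cycle 2 Day 1 is study Day 29 and Cycle 2 Day 22 is Day 50. Visit 1 is due on Day 78 (gap 49) and visit 2 on Day 106 (gap 77).

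Two missed follow-up visits would give 77 + 28 = 105 days after a Day 22 last dose and 70 + 28 = 98 after Day 15. At this transition, therefore, 65 falls below the one-missed value instead of between one and two.

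**Deaths.** After a Day 22 last dose with visit 1 missed, visit 2 is not due until day 77. A death on days 66 to 76 is censored with exactly one assessment missed. After Day 15 the corresponding days are 66 to 69.

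**Permitted delays, with one missed visit.**

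- On treatment, a cycle starting 14 days late: 28 + 14 + 28 = 70. Protocol 9.1.4 makes the day of resumption the new Day 1.
- Within follow-up, the next visit at its latest: 28 + 28 + 2 + 14 = 72.

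Both exceed 65, but each needs the longest permitted delay on top of a missed visit.

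**The case against.** **The limit is sound for most records.** This stands. With even spacing and ordinary windows it does what the SAP says, and a last dose on Day 1, or nominally on Day 8, causes no difficulty.

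**Few subjects can be affected.** Also fair. The subject must stop without progression after a Day 15 or Day 22 dose, miss visit 1, have no unscheduled assessment in between and start no new therapy. The event must then be dated beyond day 65. SAP 7.3.3 uses the investigator's date of progression, so progression found at visit 2 may be dated early enough to count. That route does not help with deaths.

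**Little rests on it.** PFS, TTP and DoR are secondary and descriptive, and DoCB is an additional variable. SAP 9.2 tabulates PFS censoring reasons with reasons for discontinuation, so PFS cases should be visible. EFS has no 65-day rule. All of this limits the consequence, but the rule still does not do what the SAP says it does.

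A reader might also infer more than the documents support:

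- *That events soon after stopping are lost.* They are not. Day 65 is 65 − 21 = 44 days after a Day 22 last dose and 65 − 14 = 51 days after a Day 15 last dose. Events up to then count, as does progression found at visit 1.
- *That a subject who misses nothing is censored.* A late visit 1 after a Day 22 last dose gives 49 + 2 + 14 = 65, which is not above 65. The delay allowance is in any case placed under visit 2 and later visits.
- *That the censoring is informative because such subjects stopped for toxicity or frailty.* The documents give no reasons or frequencies for stopping without progression.
- *That the 29-day basis causes the problem.* It does not: a limit of 63 would censor slightly more.

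**Conclusion.** The point holds for the treatment-to-follow-up transition. There, one missed visit gives 77 days (73–81) or 70 days (66–74), so a limit described as two or more missed assessments is passed after one. It also holds, as an extreme case, when one missed visit coincides with the maximum permitted delay (70 or 72 days). It does not hold for regular 28-day spacing.

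The direction is towards higher later estimates of PFS, TTP, DoR and DoCB. The size cannot be given, because the documents do not say how many subjects miss visit 1 and then progress or die. The number is probably small. However, SAP section 5 allows a recommended-dose group of 9, where one subject is 1/9, or about 11%, and SAP 9.2 reads event percentages for PFS and TTP off the curve at 2, 4 and 6 months.

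The conclusion assumes visits due as the protocol schedules them, no unscheduled assessment in the interval, and that the last row of each table takes precedence over the other rows on death. The SAP does not state an order of precedence.

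**What to change.** In the last row of SAP Tables 2 and 3, replace the 65-day criterion with a count. Censor only when two or more consecutive scheduled response assessments (Day 1 of a cycle; follow-up visits 1, 2 and so on) were missed. Take due dates from the subject's actual cycle starts and last dose, plus the permitted windows and delays. This carries out the intention the SAP already states.

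If a fixed limit is preferred, set a separate one for the move from treatment to follow-up: above 81 days after a Day 22 last dose and above 74 after Day 15. Those figures cover the visit windows only. A visit 2 that is also 14 days late would fall at 81 + 14 = 95 or 74 + 14 = 88, which is why the count is the better choice. In either case, bring the 29-day cycle into line with the 28-day cycle.

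The cost is a few lines of SAP text and a derived variable for assessments due. No data collection or clinical procedure changes. SAP 4.3 plans to re-run all analyses for follow-up, so the corrected rule could be applied there.

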## 10.1.14 End of Study (EOS) Visit

The EOS visit will occur after confirmed disease progression, or after withdrawal from the study for other reasons, or at a maximum of 3 years from the first study drug administration. The EOS visit will occur at least 28 days after last study drug administration but should be performed before any new MM therapy starts, whichever occurs first.

At the EOS visit, the following will be obtained, performed, or assessed:

- Toxicity/AE assessment since the last visit
- Concomitant medications
- Karnofsky performance status
- Blood sample for hematology, serum chemistry, coagulation, βHCG pregnancy test for women of childbearing potential, MOR03087 pharmacokinetics (only if subject had no follow-up visit), endocrinology, anti-MOR03087 antibodies, B, T, and NK cells, serum M-protein, and serum FLCs
- Urine sample for urinalysis
- Sample from 24-hour urine for urine M-protein
- Bone skeletal survey by x-ray, CT, or MRI imaging (where medically indicated, as a regular assessment of standard of care in subjects with relapsed or refractory MM)
- Response assessment
- Physical examination (including basic neurological examination of general motor and sensory systems, mental status, cranial nerves, and coordination)
- Ocular examination by an ophthalmologist (including distance visual acuity, optical coherence tomography [if available], and ophthalmoscopy under full mydriasis [if optical coherence tomography is unavailable])
- Body weight
- Quality of life questionnaires (QLQ-MY20 and QLQ-C30)
- 12-Lead ECG
- Vital signs (blood pressure, pulse rate, respiratory rate, and body temperature)
- Documentation of subject's subsequent anti-myeloma therapy, as appropriate

For subjects receiving POM or LEN, the additional following will be obtained, performed, or assessed:

• Clinical review of signs/symptoms for possible VTEs in subjects treated with POM or LEN. Subjects who develop symptomatic deep vein thrombosis will be assessed and diagnosed objectively by Doppler ultrasonography or a comparable method per institution's standard of care. See Appendix 18.9 for deep vein thrombosis and pulmonary embolism diagnostic algorithms

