Part E: MOR03087 (weekly/biweekly treatment) in combination with LEN+DEX

- Dose level 7e: 8.0 mg/kg
- Dose level 8e: 16.0 mg/kg

Each 28-day cycle will consist of:

MOR03087 infusion on Days 1, 8, 15, and 22 of the cycle. In Cycle 1, a loading dose will additionally be administered on Day 4 of the cycle.

Only for dose level 8e, for cycle 4 and onwards each 28-day cycle will consist of: MOR03087 infusion on Day 1 and 15 of the cycle.

Subjects who have received treatment beyond Cycle 3 will be switched to the biweekly schedule at the next Day 1 or Day 15 visit. In exceptional cases, and after discussion between the investigator and the sponsor, the treating physician may determine that it is in the best interest of the subject to remain on the weekly MOR03087 schedule, in which case the sponsor should be informed accordingly.

Oral LEN 25 mg on Days 1-21 of the 28-day cycle.

Oral DEX 40 mg (\leq 75 years old) or 20 mg ($>$ 75 years old) on Days 1, 8, 15, and 22 of the

28-day cycle.

For subjects in Cohort 8e who switch to biweekly MOR03087 treatment from Cycle 4 onwards, the DEX treatment schedule will remain unchanged (Day 1, 8, 15 and 22).

In Cycle 1 DEX is to be added to the loading dose on Day 4.

Following completion of Parts D and E (dose escalation of MOR03087 in combination with POM + DEX and LEN + DEX), the MTD and/or recommended dose in each part will be confirmed in a minimum of 6 subjects.

All cohorts:

Based on the individual risk/benefit ratio, subjects who have an ongoing response of at least stable disease (SD) may continue treatment with the assigned study regimen until disease progression or until a maximum of 3 years after first treatment. In case subjects present with progressive disease or with no better status than SD after 4 treatment cycles starting with Cycle 1 Day 1, the investigator may add a low weekly dose of DEX to the regimen at his/her discretion, provided DEX is not already part of the treatment regimen.

After study drug discontinuation due to reason other than disease progression and other than withdrawal of consent, all subjects will return for a follow-up visit 1 and follow-up visit 2. Further follow-up visits will be conducted at 4-week intervals until the subject is progressive, begins subsequent anti-myeloma therapy, or dies.

All subjects will be followed up for a maximum of 3 years after first administration of study drug.

Dose Escalation Process:

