Event-free survival (EFS): EFS will be defined as the time from Cycle 1, Day 1 until date of progression, date of death, or date of discontinuation of treatment for any reason (e.g. toxicity, subject preference, or initiation of a new treatment without documented progression), whichever occurs earlier. Subjects still on treatment, without disease progression, will be censored at the date of the last available tumor assessment.

Additional time to event variables for the subgroup of responders:

Time to first response: Time to first response will be defined as the time from Cycle 1, Day 1 until start date of first response (sCR, CR, VGPR or PR).

Time to best response: Time to best response will be defined as the time from Cycle 1, Day 1 until best response (sCR, CR, VGPR or PR).

Time to first clinical benefit: Time to first clinical benefit will be defined as the time from Cycle 1, Day 1 until first clinical benefit (sCR, CR, VGPR, PR or MR).

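### The EFS definition has no exception for treatment that ends at the 3-year maximum or at study closure, so a progression-free subject who stops for that reason is scored as an event although PFS censors the same subject

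*SAP*

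**What the plan says.** **EFS event.** SAP 7.3.3.3 runs EFS from Cycle 1 Day 1 to the first of progression, death and "date of discontinuation of treatment for any reason". The reasons it then gives in brackets (toxicity, the subject's preference, a new therapy begun before progression is documented) are examples only, and no exception follows.

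**EFS censoring.** There is one rule: "Subjects still on treatment, without disease progression, will be censored at the date of the last available tumor assessment". EFS has no censoring table; Table 2 covers DoCB, DoR and TTP, and Table 3 covers PFS.

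**Length of treatment.** SAP 3.1 lets subjects with at least stable disease continue "until disease progression or until a maximum of 3 years after first treatment". Protocol 7.1 has the same limit.

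**Length of follow-up.** SAP 3.1: "All subjects will be followed up for a maximum of 3 years after first administration of study drug". Protocol 10.1.14 places the end-of-study visit after progression, after withdrawal, or "at a maximum of 3 years from the first study drug administration", and adds: "The EOS visit will occur at least 28 days after last study drug administration".

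**Analysis.** SAP 9.2 gives EFS the same Kaplan-Meier presentations as TTP and PFS: number and percentage with an event, median, quartiles, estimates at 2, 4 and 6 months, and a plot for combined data.

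**The concern.** A subject who reaches the 3-year limit without progression has not failed treatment; the plan ended it. The EFS rule does not separate this stop from one for toxicity or patient choice. Because the subject is no longer on treatment, the only censoring rule cannot apply, and the any-reason clause makes the subject an event. The same happens if the sponsor terminates the study, which protocol 8.7.1 and 8.7.2 allow.

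The number and percentage of EFS events and the right-hand end of the EFS curve would then partly reflect an administrative limit. The report would show the same subject as progression-free and censored in the PFS table and as a failure in the EFS table, with no clinical event between the two.

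**Working it through.** **Plan's own figures.** The plan states none for EFS. Its only calculation for the recommended-dose group of at least 9 subjects (protocol 15.9) concerns adverse events, and it reproduces: 1 − 0.83^9 = 0.813 (stated 81%) and 1 − 0.77^9 = 0.905 (stated 90%). Only the group size is used below.

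**Step 1: apply the rules to one subject who stops at the limit, progression-free and alive.**

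| Endpoint | Rule that applies | Result |
|---|---|---|
| PFS (SAP Table 3) | No progression: "Date of last tumor assessment" | Censored |
| TTP, DoR (SAP Table 2) | No progression: same date rule | Censored |
| EFS (SAP 7.3.3.3) | Off treatment, so the censoring rule fails; any-reason clause applies | Event |

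**Step 2: when the EFS event falls.** Assumption: 30.4375 days per month.
- Limit: 3 × 365.25 = 1095.75 days; 1095.75 / 30.4375 = 36.0 months.
- If the end-of-study visit must fall within 3 years and at least 28 days after the last dose, the last dose falls by (1095.75 − 28) / 30.4375 = 35.1 months.
- The event therefore lies at about 35.1 to 36.0 months. It cannot be fixed more closely because the SAP does not define the discontinuation date.

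**Step 3: effect on the Kaplan-Meier estimate.** Assumptions: n = 9; k subjects reach the limit; the other 9 − k have earlier events, spread evenly before 34 months; no other censoring. The value of k is illustrative, since the documents give no treatment durations. After the earlier events the curve stands at k/9. Under the rule as written, all k then have events and it falls to 0. If they are censored, it ends at k/9 and the event percentage is (9 − k)/9.

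| k | Event %, as written | Event %, censored | Curve end, as written | Curve end, censored | Median, as written / censored (months) | 75% quantile, as written / censored (months) |
|---|---|---|---|---|---|---|
| 1 | 100 | 88.9 | 0 | 0.111 | 18.9 / 18.9 | 26.4 / 26.4 |
| 2 | 100 | 77.8 | 0 | 0.222 | 21.2 / 21.2 | 29.8 / 29.8 |
| 3 | 100 | 66.7 | 0 | 0.333 | 24.3 / 24.3 | 36 / not reached |
| 5 | 100 | 44.4 | 0 | 0.556 | 36 / not reached | 36 / not reached |

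The 75% quantile is the first time the curve is at or below 0.25, so without other censoring it moves only when k/n exceeds 25%. The median moves only when k/n exceeds 50%. With n = 18, 3 at the limit (16.7%) leave the 75% quantile at 29.8 months under both rules, while 5 (27.8%) change it from 36 months to not reached. These are point estimates; confidence limits were not calculated.

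**Step 4: what cannot change.** The 2-, 4- and 6-month estimates lie long before the limit and are identical under both rules.

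**The case against.** **An all-cause discontinuation endpoint is legitimate.** Shown beside PFS, it can be a deliberate choice. That stands, and the any-reason clause need not go. What is missing is a rule for a stop that the plan itself imposes.

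**Completing the maximum may not count as discontinuation.** All the SAP's examples are early stops, so a programmer might read it this way. The SAP does not say so. On that reading the subject is neither an event nor still on treatment, and EFS has no rule for the case, so a sentence is needed either way.

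**The limit is not stated everywhere.** The protocol synopsis, 4.2 and 10.1.13 describe continued treatment without a 3-year maximum, whereas protocol 7.1 and SAP 3.1 state one. These passages must be reconciled. Administrative ending remains in any case, because follow-up is limited to 3 years.

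**The consequence is small.** This largely stands. EFS is not among the endpoints in protocol section 11 or SAP 2.2; the SAP lists it as an additional variable and the analysis is descriptive. The final analysis can be triggered once all subjects reach Cycle 3 Day 1 (SAP 4.2), and subjects still on treatment then are correctly censored. The effect falls mainly in the follow-up re-run (SAP 4.3). Its dictionaries are dated March 2020 (SAP 8.3) against a July 2017 protocol, so 3-year data are plausible there.

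A reader might also infer more than the documents support:
- That the upper EFS quantiles are generally understated. With 2 of 9 at the limit, neither the median nor the 75% quantile moves.
- That a plateau beyond 3 years is lost. Follow-up ends at 3 years, so neither rule gives information after it; only the last step of the curve differs.
- That the combination parts are worst affected. Neither document gives treatment durations by part.

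**Conclusion.** The EFS rule as written gives a wrong result for subjects whose treatment ends administratively without progression or death. Applied literally and with complete follow-up, it forces the event rate to 100% and the curve to 0 by about 36 months, whatever the treatment does. Under the assumptions stated (n = 9, no other censoring), the curve ends at 0 instead of 11%, 22% or 33% when 1, 2 or 3 subjects reach the limit.

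The event count, the percentage with an event and the end of the curve are affected whenever anyone reaches the limit; the quantile point estimates move only above the thresholds shown. PFS, TTP and DoR are not affected. The point is minor in weight, because EFS is additional and descriptive, but the rule needs correcting before the follow-up analyses are run.

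**What to change.** Add to the EFS paragraph in SAP 7.3.3.3 that a subject whose treatment ends because of the 3-year maximum or closure of the study, without progression or death, is censored at the last tumor assessment, in line with Table 3. Define the discontinuation date in the same place.

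Identify these subjects by the recorded reason. SAP 8.1 and 9.2 refer to study discontinuation reasons, but whether the eCRF has a category for reaching the maximum duration cannot be verified from the documents. If it has none, use the treatment dates and the study closure date.

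Reconcile the protocol synopsis, 4.2 and 10.1.13 with protocol 7.1 and SAP 3.1 on the 3-year maximum. The statistical change costs one censoring sentence, one date definition and a small programming change; it needs no new data and no change in patient care.
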